# 3 Introduction

#### Overview

## The problem: I am feeling ill during the weekend, where should I go?

When confronted with an unexpected illness during the weekend, patients can go either to the emergency department (ED) of a hospital or to the general practitioner (GP) on call. In Flanders, the GPs often organise this on call service for a specified region in a central location called General Practice Cooperatives (GPC, "Wachtpost" in Dutch). Patients do not know the characteristics of these different out of hours (OOH) services and find it hard to estimate the urgency of their own complaints. Therefore, many patients with presentations suitable for primary care go directly to the ED. This leads to additional costs for both government and patient, long waiting times at the ED and a high workload for the emergency physicians in Flanders.

#### Aim of this project: we will advise you where to go

The aim of this project is to deliver the most appropriate care for patients presenting at the ED. To achieve this objective a triage nurse will assess all patients presenting at an ED and advise them on the most appropriate point of care: GPC or ED. Triage is 'the sorting out and classification of patients to determine priority of need'. Extended triage is triage combined with allocation to either ED or GPC, which is new in Flanders.

Many EDs in Flanders use the Manchester Triage system (MTS) in their regular care for triage within the ED, to sort patients according to the urgency of their presentation. We developed an extended MTS (eMTS) which foresees allocation to either ED or GPC. Scientific research is crucial to evaluate such triage systems before implementation is possible. Our study is a cluster-randomised trial. During one year, we will perform extended triage using the eMTS at one ED/GPC collaboration. Every month one weekend will serve as a control: the patient does not get an allocation advice.

# Scientific methodology of this project: is this service at this time the most appropriate for me?

[figure not shown]
Three aspects determine the most appropriate OOH service for a specific patient at a specific time:

- Medical aspects: is this service capable of handling the medical problem in an efficient and qualitative way? Is it safe?
- Financial aspects: is it the most cost effective service for both government and patient?
- *Process aspects:* can the delivered service satisfy the perceived needs of patients and staff? What are the major barriers and facilitators? What can we learn from reported incidents? How can we improve safety? This aspect is only briefly described in this protocol, as we will make a separate protocol.

# Study sites and partners

The TRIAGE-trial is a collaboration between the University of Antwerp, Antwerp University Hospital, clinicians at a GPC (Antwerpen Oost) and the ED of a general hospital (AZ Monica Deurne).

#### **eMTS**

The Manchester Triage System (MTS) is one of the most commonly used triage systems in Europe(1). It enables nurses to assign a clinical priority to patients, based on presenting signs and symptoms, without making any assumption about the underlying diagnosis. The MTS assigns patients to one out of five urgency categories, which determine the maximum time to first contact with a physician (2). In the TRIAGE-trial, we will use an extended MTS (eMTS): we did not change the MTS but added some extra questions to allow allocation to ED or GPC. Because of legal and practical reasons, we have decided to allow allocation to primary care only for the two lowest urgency categories. The patients in the green category (called standard urgency) have to see a doctor within two hours. For the blue category (called non-urgent) the maximum period is four hours. In Figure 1, we demonstrate the eMTS flow chart for shortness of breath in children.

Figure 1: eMTS flow chart for shortness of breath in children. The orange arrows and boxes are the extension.

# 4 Research Approach

## A diagnostic Intervention

A nurse will see the patient ideally within ten minutes after arriving at the ED. The nurse will classify a patient's presentation using the MTS, which will enable to make a categorisation of urgency. If the patient's urgency category is either blue or green, the nurse will use the eMTS to assess suitability for primary care. This assessment depends on the presentational flow chart used: for some flowcharts, all or none of the blue/green presentations will be referred to primary care, for others the nurse has to ask additional questions. The result of this extended triage is a shared decision of the patient and the nurse: the patient is (or is not) eligible for primary care. Because not all possible questions and signs are incorporated in the eMTS the triage nurses will have the possibility to overrule the eMTS advice in both directions. An adapted registration system will help the nurse select and follow the correct flowchart and will give an eMTS advice once all questions have been assessed. Patients will have the right to refuse the advice of the nurse without any further consequences for their treatment at the ED. We will provide all participating nurses and physicians with a detailed manual in Dutch about the intervention and the research protocol. Our entire eMTS is also available as a separate file.

# Hypotheses and Research questions

#### Medical aspect

Our primary hypothesis: the extended triage intervention will lead to a substantial increase in the proportion of patients seen by the GP.

Without the intervention, all study patients can be divided in three categories: seen by ED, seen by GPC and left without being seen (after the triage). By adding the compliance of the patient to the allocation advice we get the following table:

	Patient goes to GPC	Patient goes to ED	Left without being seen
Advice GPC	Compliant patient GPC	Non-compliant patient GPC	Left without being seen type 1
Advice ED	Non-compliant patient ED	Compliant patient ED	Left without being seen type 2

Table 1: patient categories

The proportion of study patients seen at the GPC is a combination of patients compliant to a GPC advice and patients not compliant to an ED advice. The latter category will probably be small.

#### *Research question:*

- 1. What is de the difference in the proportion of study patients seen by the GP between intervention and control weekends?
  - 1.1. Is this proportion associated with the patient's presentation (chosen eMTS flowchart and urgency)?
  - 1.2. Is this proportion associated with the occupancy rate of the ED and/or GPC?
  - 1.3. Is this proportion associated with the operating triage-nurses and/or the operating emergency physician?
  - 1.4. Is this proportion associated with the patient's background characteristics? (sex, age, community, insurance status)?
  - 1.5. Is there seasonal variation in this proportion?

Secondary hypothesis: a nurse using the eMTS is able to detect primary care patients. We can assess the correctness of the nurse's allocation advice as a diagnostic instrument.

The results of the triage consult is either a GPC or ED advice. Arbitrarily we will call a GPC advice a positive diagnosis. The gold standard is the opinion of the physician (either emergency physician or GP) after the consultation. This standard is used in almost all of the literature(3), as no better gold standard is available. We are aware of some disadvantages: this opinion depends on the personality and other characteristics of the treating physician and some patients have presentations suitable for both ED and GPC. On the other hand, agreement between nurse and physician is important for the feasibility of extended triage.

The way we will measure the correctness of the triage advice depends on whether the patient is compliant to this advice. This makes Table 1 more complex:

	Patient goes to GPC		Patient goes to ED	
Opinion physician	GPC correct	Had to go to ED	ED correct	Had to go to GPC
Advice GPC	Correct decision 1	False positive 1	False positive 2	Correct decision 2
Advice ED	False negative 1	Correct decision 3	Correct decision 4	False negative 2

Table 2: patient categories for the eMTS as a diagnostic instrument

Because our eMTS is risk adverse, we already know we will have a certain amount of false negative 2: patients who are compliant to the advice of ED although they had to go to the GPC according to the emergency physician. This category is not our primary focus.

We are mostly interested in false positive 1: patients who complied with the advice GPC but should have stayed at the ED. Some of these patients might be subject to a safety risk. For example, a patient with a heart attack allocated to the GPC might lose valuable time. This category is the same as the proportion of study patients allocated to the GP but referred back to the ED. We will give this category special attention in our process analysis.

Finally, we are also interested in the category correct decision 2: patients who are not compliant to a correct GPC advice. These patients made an inefficient decision so there is room for improvement.

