#### *Research questions:*

- 2. What is the validity of the eMTS as a preliminary diagnostic instrument to detect a primary care patient?
  - 2.1. What is the proportion of correct extended triage decisions measured by comparing the triage advice with the urcenty evaluation of the physician?
  - 2.2. What is the proportion of correct extended triage decisions with advice GP measured by the proportion of referrals within this category?
  - 2.3. What is the proportion of patients wrongly assigned to GPC (all false positives)?
  - 2.4. What is the proportion of patients wrongly assigned to GPC who did go to the GPC (type 1 false positives)
- 3. What is the proportion of patients who are not compliant to a correct GPC advice (Correct decision 2).
  - 3.1. What are the determinants for this non-compliance? (same determinants as studied in question 1.1-1.4)
- 4. What is the proportion of patients in which the nurse gives another advice comparing to the eMTS?
- 5. Does the intervention influence the number of patients left without being seen?
- 6. What is the shift in workload during the different phases of this study for all participating healthcare providers (GPs, triage nurses and ED physicians)?
- 7. Does the epidemiology in terms of reasons for encounter and diagnoses at both OOH services differ between intervention and control weekends?
- 8. What is the proportion of patients who return to the ED within two weeks for each of the categories described in table 2?

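### Question 2 asks whether the nurse detects primary care patients, but none of sub-questions 2.1 to 2.4 reports sensitivity or the false negatives defined in Table 2

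*Combined protocol and SAP*

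**What the plan says.** The secondary hypothesis, under Hypotheses and Research questions (Medical aspect), reads "Secondary hypothesis: a nurse using the eMTS is able to detect primary care patients". The direction of the test is fixed by "Arbitrarily we will call a GPC advice a positive diagnosis", and the reference by "The gold standard is the opinion of the physician (either emergency physician or GP) after the consultation". Table 2 then crosses advice, destination and physician opinion, giving Correct decisions 1 to 4, False positives 1 and 2, and False negatives 1 and 2.

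Question 2 repeats the aim: "What is the validity of the eMTS as a preliminary diagnostic instrument to detect a primary care patient". Its sub-questions are:

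- 2.1: overall agreement, the share of all triage decisions that match the physician's evaluation.
- 2.2: correctness within GPC advice, judged by how many of those patients are referred.
- 2.3: "What is the proportion of patients wrongly assigned to GPC (all false positives"
- 2.4: the type 1 false positives, meaning those who actually went to the GPC.

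Of False negative 2 (patients who followed ED advice although the emergency physician judged them suitable for the GPC), the protocol says that it will occur because the eMTS is cautious, and adds "This category is not our primary focus".

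Methodology for the medical aspect measures correctness at the GPC by referrals to an ED. At the ED, correctness is the share of all patients staying there for whom the physician says that the GPC would have been better.

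**The concern.** With GPC advice as the positive result, detecting primary care patients means finding a high share of those whom the reference calls primary care patients. Every measure of that kind has the reference-positive patients as its denominator. None of 2.1 to 2.4 does, and the ED correctness ratio does not either.

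The protocol expects the cautious eMTS to miss primary care patients. That expected weakness bears directly on the hypothesis, yet no planned measure isolates it. The trial could report few false positives and fair overall agreement, and leave open what share of primary care patients the nurse identified.

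**Working it through.** **Planned measures against the cells of Table 2** (CD = correct decision, FP = false positive, FN = false negative)

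- 2.1: (CD1 + CD2 + CD3 + CD4) / all patients. False negatives count as errors, but are pooled with everything else.
- 2.2: CD1 / (CD1 + FP1), judged by referrals.
- 2.3: FP1 + FP2. The denominator is not stated; I take all patients.
- 2.4: FP1. Same remark.
- ED ratio: (CD2 + FN2) / all patients staying at the ED. A yes from the physician is a correct decision if the patient had been advised to go to the GPC, and a miss if advised to stay. The ratio pools the two.
- Sensitivity, not planned: (CD1 + CD2) / (CD1 + CD2 + FN1 + FN2).

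The documents give no figure for question 2 and no prevalence of primary care patients, so there is nothing to reproduce. All inputs below are assumptions.

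**How far overall correctness and sensitivity can differ.** Let p be the prevalence, a the share advised to the GPC and v the share of that advice that is correct. Then TP = a·v, FP = a(1 − v), FN = p − TP and TN = 1 − p − FP. Overall correctness is TP + TN = 1 − p + a(2v − 1), and sensitivity is a·v / p.

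Example with p = 0.40, a = 0.15, v = 0.95:

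- TP = 0.1425, FP = 0.0075, FN = 0.2575, TN = 0.5925
- Overall correctness = 0.1425 + 0.5925 = 73.5%
- Sensitivity = 0.1425 / 0.40 = 36%

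Range over p = 30% to 50%, a = 10% to 25%, v = 90% to 95%:

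- Lowest (p = 0.5, a = 0.10, v = 0.90): correctness 0.5 + 0.10 × 0.8 = 58%; sensitivity 0.09 / 0.5 = 18%
- Highest (p = 0.3, a = 0.25, v = 0.95): correctness 0.7 + 0.25 × 0.9 = 92.5%; sensitivity 0.2375 / 0.3 = 79%

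**Which measures favour rare GPC advice.** Triage A almost never advises the GPC (sensitivity 2%, specificity 99.9%). Triage B is useful (sensitivity 70%, specificity 90%). Compliance with GPC advice is set at 90%, whether or not the advice is correct. Each cell shows A / B, in percent.

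| Prevalence | 2.1 correct | 2.2 correct within GPC advice | 2.3 all FP | 2.4 type 1 FP |
|---|---|---|---|---|
| 10% | 90.1 / 88.0 | 69.0 / 43.8 | 0.09 / 9 | 0.08 / 8.1 |
| 20% | 80.3 / 86.0 | 83.3 / 63.6 | 0.08 / 8 | 0.07 / 7.2 |
| 40% | 60.7 / 82.0 | 93.0 / 82.4 | 0.06 / 6 | 0.05 / 5.4 |
| 60% | 41.2 / 78.0 | 96.8 / 91.3 | 0.04 / 4 | 0.04 / 3.6 |

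A beats B on 2.2, 2.3 and 2.4 in every row. On 2.1 it beats B only at 10%. A rule that never advises the GPC scores 1 − p on 2.1 and zero on 2.3 and 2.4; 2.2 is then undefined. The result for 2.2 depends on the assumed specificities: it favours advice confined to the clearest cases, and does not reward rarity as such.

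**Precision of sensitivity.** Recruitment strategy and expected dropout gives 8000 weekend patients in 2016. At prevalence 10%, 30% or 50% that is 800, 2400 or 4000 primary care patients. For a sensitivity of 50%, the 95% half-width is 1.96 × √(0.25 / n) = 3.5, 2.0 or 1.5 percentage points. This counts all weekends and ignores clustering, so it is optimistic.

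**The case against.** A reader might infer that a triage which almost never advises the GPC would score well on question 2 and could be presented as a success. The documents do not support that.

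- 2.1 counts every false negative as an error. A never-GPC rule scores 60% at a prevalence of 40%. It looks good only if few patients are primary care patients, and the Overview says that many are.
- The primary hypothesis expects a substantial rise in the proportion seen by the GP. Such a triage would fail it. That outcome still does not measure detection: it combines advice with compliance and has no reference standard.

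Sensitivity can also be reconstructed. With all patients as denominator, the false negatives are 1 − (2.1) − (2.3). In the example this is 1 − 0.735 − 0.0075 = 0.2575; with 15% advised, sensitivity is 0.1425 / 0.40 = 36%. Question 8 needs every Table 2 category as a denominator, and the list of proportions in Methodology for the medical aspect is open-ended. This stands: the information will exist. But a quantity that a reader must derive, using denominators the protocol does not state, is not the planned answer to question 2.

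The emphasis on False positive 1 is a disclosed and reasonable safety choice. The eMTS section allows allocation to primary care only for green and blue, so sensitivity over all patients is partly capped by rule and not by the nurse's ability. Any pooled sensitivity also joins two references: referral at the GPC and the physician's answer at the ED. Both limits stand and belong in the fix.

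**Conclusion.** The gap is real but narrow. The secondary hypothesis and question 2 are about detection, and no planned measure conditions on the patients whom the physician judges to be primary care patients. Sub-questions 2.3 and 2.4, and largely 2.2, favour rare GPC advice. Sub-question 2.1 penalises misses, but to a degree set by prevalence.

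Over the assumed range, overall correctness and sensitivity reach their extremes at the same two corners, so the point is not that high correctness always hides low sensitivity. It is that correctness does not reveal sensitivity: 73.5% correct can go with 36% detected. The size rests on assumed prevalence, advice rate and correctness of advice, because the protocol gives none of these. That sensitivity is absent from 2.1 to 2.4 rests on no assumption.

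**What to change.** Answer question 2 with two ratios from Table 2:

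- Sensitivity = (Correct decision 1 + 2) / (Correct decision 1 + 2 + False negative 1 + 2)
- Specificity = (Correct decision 3 + 4) / (Correct decision 3 + 4 + False positive 1 + 2)

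Give confidence intervals that allow for clustering by weekend and nurse, using the mixed model already planned. Report both ratios for all patients and again within the green and blue categories, where GPC advice is possible. State that the reference is referral to an ED for patients at the GPC and the physician's answer for patients at the ED. Keep 2.1 to 2.4 and the safety focus on False positive 1 as supporting results, and state their denominators.

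This supplies the right estimate but no pass mark. If the hypothesis is to be tested and not only described, the investigators must also state in advance what sensitivity they would accept.

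The cost is two ratios and a short paragraph. Every cell is already defined, and the physician's question is already put for all patients at the ED, so no new data are needed.

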#### Design of the clinical trial

#### A controlled longitudinal prospective intervention trial

To answer the above-mentioned research questions we need a longitudinal prospective intervention trial.

To allow definitive conclusions for our questions we need a control group. Historical controls will have too much confounding (not all data is available, the ED was organised in a different way, the GPC was unknown for many patients). Individually randomised controls are impossible from a practical point of view and because of contamination (patients will talk to each other and will not understand why some get a GPC advice and others not). Finally, randomisation by shift is not possible because they overlap in time. Therefore, randomisation is only possible by weekend. We will roll out one control weekend out of every four intervention weekends.

During a control weekend, all data registration and collection will be the same as during intervention weekends but we will not inform patients about their allocation advice. The emergency physician will see all patients deciding to stay at the ED, without influence of the triage advice. As in standard clinical care, patients will have the right to change their mind and go spontaneously to the GPC. Another difference is the communication to the patient: during intervention weekends, we will inform them about the intervention using leaflets and broadcasting in the waiting room of the ED. During control weekends, we will only inform about MTS-triage in general but no about the GPC. We will always mention the iCAREdata opting-out procedure.

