# Methodology for the medical aspect

The data necessary for this work package are part of a routine clinical report. We will use three types of these reports: triage-consultation reports, ED consultation reports and GPC consultation reports. We will collect these data using the iCAREdata database. This database can link our three types of clinical reports using an irreversibly coded national number. Due to data protection rules, the iCAREdata data manager will execute all queries and only aggregated results will be transferred to the researchers. For more complex statistical analysis, the data manager will transfer an analysis specific table or the analysis will be carried out on the computer of the data manager in cooperation between the researcher and the data-manager. A detailed data management plan is available. The correctness of a triage decision depends on the patient's situation:

- At the GPC (patients compliant to a GPC advice or non-compliant to an ED advice): the ratio of patients referred to an ED to the total number of patients coming from the ED of AZ Monica.
- At the ED (patients compliant to an ED advice or non-compliant to a GPC advice): the physician will answer the same question for all patients: "Should this patient better go to the GPC?". The correctness is defined as the ratio of the patients with a positive answer to this question to the total number of patients staying at the ED after triage.

The parameters of interest in questions 1 through 8 are (conditional) proportions, which calls for analysis by a non-linear model (e.g. binary logistic regression). The study design results in the creation of nested data, where patients are nested in weekends, and weekends are nested in (multiple) nurses. Appropriate analysis of such auto-correlated data requires a nonlinear mixed model. During the first months, data will be used to produce point-estimates of these proportions (e.g., patients seen by GP, correct triage decisions, all false positives, type 1 false positives, patients left without being seen, etc.). With increasing duration of the study, incoming data will be used to explain variability of these probabilities in terms of patient background characteristics, operating nurses/emergency physician, season, etc. Statistical assistance will be called for in order to conduct these analyses.

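### Questions 2.1 and 2.3 pool two reference standards in proportions set by patient compliance, so the pooled eMTS validity does not measure triage accuracy alone

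*Combined protocol and SAP*

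**What the plan says.** All references are to the combined protocol and SAP, section 4.

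- **Nominal standard** (Hypotheses and Research questions, secondary hypothesis): "The gold standard is the opinion of the physician (either emergency physician or GP) after the consultation". The same text then says: "The way we will measure the correctness of the triage advice depends on whether the patient is compliant to this advice".
- **Measure at the GPC** (Methodology for the medical aspect): "the ratio of patients referred to an ED to the total number of patients coming from the ED of AZ Monica". The discussion of type 1 false positives agrees: "This category is the same as the proportion of study patients allocated to the GP but referred back to the ED".
- **Measure at the ED** (same section): the emergency physician answers, for every patient, "Should this patient better go to the GPC".
- **Pooled questions:** 2.1 asks for one overall proportion of correct decisions, obtained by "comparing the triage advice with the urcenty evaluation of the physician". Question 2.3 counts all false positives, which in Table 2 means type 1 (patient at the GPC) plus type 2 (patient at the ED).
- **Destination-specific questions:** 2.2 uses referrals only, and 2.4 counts type 1 false positives only.
- **Control weekends** (Design of the clinical trial): data registration is unchanged and patients are not told their advice. "The emergency physician will see all patients deciding to stay at the ED, without influence of the triage advice".
- **Blinding** (Randomisation procedure): participants, staff and researchers cannot be blinded.

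**The concern.** Referral is a behaviour; the ED question records an opinion. A GP who thinks the ED would have been the better place, but manages the patient anyway, counts as confirming the advice. An emergency physician with the same doubt counts as contradicting it. On intervention weekends, advice and patient choice together decide which measure applies. This is differential verification.

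The disadvantages that the plan lists for its gold standard are variation between physicians and patients suited to both services. Neither covers a standard that changes with destination. Question 2.1 adds a further loose end: it names an urgency evaluation for which the methodology section defines no measure.

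At stake is the validity figure that others would use when deciding whether to adopt the eMTS. A site with the same triage but different compliance could obtain a different figure. The primary question, the proportion of patients seen by the GP, is not affected.

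**Working it through.** The plan states no validity, compliance, referral or agreement rate, so there is no figure to reproduce. All values of c, r, b, q and g below are assumptions.

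**1. Triage fixed, compliance varied.** Among patients advised GPC, let c be compliance, r the referral rate at the GPC, and b the share whom the emergency physician says should go to the GPC.

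Pooled correctness = c(1 − r) + (1 − c)b

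- r = 7%, b = 70%, c = 50%: 0.5 × 0.93 + 0.5 × 0.70 = 81.5%.
- Same r and b, c = 90%: 0.9 × 0.93 + 0.1 × 0.70 = 90.7%. The swing is 9.2 points.
- r = 5%, b = 70%: 77.5% at c = 30%, 82.5% at 50%, 87.5% at 70%, 92.5% at 90%.

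The shift from 30% to 90% compliance is 0.6 × [(1 − r) − b]. Over r = 2–10% and b = 50–90% it runs from 0.6 × (0.90 − 0.90) = 0 to 0.6 × (0.98 − 0.50) = 28.8 points. It vanishes only where both sites show the same apparent correctness. With 80% at each site, the pooled figure is 80.0% at every compliance.

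**2. Compliance fixed, triage varied.** Let q be the share of GPC-advised patients truly suited to the GPC. Assume that the GP refers 50% of ED-suited and 2% of GPC-suited patients, and that the emergency physician says GPC for 85% of GPC-suited and 10% of ED-suited patients. At c = 70%:

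Pooled = 0.7 × [1 − 0.50(1 − q) − 0.02q] + 0.3 × [0.85q + 0.10(1 − q)]

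This gives 91.3%, 88.5%, 82.9% and 77.3% at q = 95%, 90%, 80% and 70%. The pooled figure therefore responds to triage as well as to compliance.

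**3. Scope of the swing.** Step 1 concerns GPC-advised patients and so bears directly on 2.3. Question 2.1 also includes ED-advised patients, few of whom are expected to go to the GPC. If a share g is advised GPC and the ED-advised row is stable, the swing in 2.1 is g times as large: for 9.2 points, 0.10 × 9.2 = 0.9 to 0.50 × 9.2 = 4.6 points at g = 10–50%.

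**4. Size of the control-weekend set.** Inputs are 8000 weekend patients in 2016 (Recruitment strategy), 15 exclusions per weekend (Inclusion and Exclusion), and one control weekend a month (section 3, Aim of this project).

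- 8000/52 = 153.8 per weekend, less 15 = 138.8; × 12 = 1,666 patients (1,388 to 1,805 for 10 to 13 control weekends).
- If 10–50% are advised GPC: 167 to 833 patients.
- 95% half-width = 1.96 × √[p(1 − p) × DE/n], with p the proportion correct and DE the design effect for clustering by weekend (assumed 1 to 2).

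| n | p | DE | half-width (points) |
|---|---|---|---|
| 833 | 90% | 1 | 2.0 |
| 500 | 80% | 1 | 3.5 |
| 500 | 80% | 2 | 5.0 |
| 167 | 80% | 1 | 6.1 |
| 167 | 80% | 2 | 8.6 |

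The least favourable corner (n = 167, p = 70%, DE 2) gives 9.8.

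**The case against.** The strongest reply is that the plan already separates destinations. Table 2 splits every cell by place of care, questions 2.2 and 2.4 are destination-specific, question 8 reports by Table 2 category, and the stated main interest is the type 1 false positive. All of that stands. It confines the problem to 2.1 and 2.3, which sum over the destinations, but does not remove it.

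Several stronger readings are tempting, and the documents do not support them:

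- **That validity reflects compliance instead of triage.** Step 2 of the working shows that it reflects both.
- **That three standards are in use.** Only two are given a measure. The urgency evaluation in 2.1 is wording that was never reconciled with the methodology.
- **That question 2.2 mixes standards.** It uses referral only. It could not be answered from control weekends, when most patients should stay at the ED.
- **That physicians demonstrably know the advice.** This is plausible, since staff are unblinded and a patient arriving at the GPC from the ED suggests what the advice was. No section says that physicians are shown it, or that they are not.
- **That control weekends are free of these biases.** The sentence about no influence of the advice may mean only that care is not steered by it. Whether the physician can see the registered advice is unconfirmed.

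There is also a fair point against relying on control weekends alone. A diagnostic Intervention describes the triage result as a decision shared by patient and nurse. An advice withheld from the patient may not be quite the same index test. Control weekends should therefore supplement the intervention-weekend results, not replace them.

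**Conclusion.** The point holds for questions 2.1 and 2.3. As written, their pooled figures combine a referral standard and an opinion standard with weights set by compliance, so they do not measure triage accuracy alone. Physician knowledge of the advice is a plausible additional bias, inferred and not documented.

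The size cannot be fixed from the documents. For GPC-advised patients it depends on the gap between non-referral at the GPC and agreement at the ED: no shift if the two are equal, close to 29 points between 30% and 90% compliance at the widest assumed gap. In 2.1 it is diluted by the share of patients advised ED. Part of any observed gap may also be real, because patients who decline the advice may differ from those who accept it. Pooling hides that too.

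This is a secondary objective, and the change is worth making before the analysis is run.

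**What to change.** 1. Report 2.1 and 2.3 separately for each combination of advice and destination, with no total across the two standards. The split by advice is needed in any case: a referral from the GPC is an error after a GPC advice but a correct decision after an ED advice, and a positive answer at the ED reverses in the same way.
2. Replace the urgency evaluation in 2.1 with the ED question defined in the methodology, or define how urgency is to be measured.
3. Pre-specify a single-standard estimate for 2.1 and 2.3 from the control weekends, using the emergency physician's answer for patients who stay. Give the number who went to the GPC or left without being seen, and allow for clustering by weekend.
4. State whether the physician could see the advice, on control and on intervention weekends.
5. Leave 2.2 and 2.4 on the intervention weekends as destination-specific measures.

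The data are already to be collected, so the cost is wording and analysis time. The control-weekend estimate uses about 12 of 52 weekends, so its intervals are wider: roughly 2 to 9 points half-width over the tabulated cases. Its limitation, that the advice was not shared with the patient, should be stated beside the result.
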